6. To determine how AD skin endotypes and gene expression differ among the study outcome groups: (1) topical steroid responders, (2) dupilumab responders, (3) dupilumab non-responders, (4) non-AD, and (5) long-term dupilumab participants	8. Non-lesional and lesional skin tape endotypes determined in exploratory objective 4 9. Non-lesional and lesional skin biopsy endotypes determined in exploratory objective 4 (adults only) 10. Non-lesional and lesional skin tape transcriptome 11. Non-lesional and lesional skin biopsy transcriptome (adults only)	6. The clinical response to protocol's standard-of-care treatment among different AD participants will be associated with distinct AD skin endotypes and transcriptional profiles.
7. To determine skin gene expression changes that are associated with topical moisturizer treatment	12. Non-lesional and lesional skin tape transcriptome (long-term dupilumab participants excluded)	7. Clinical treatment with moisturizer is associated with changes in transcriptional profiles in the skin.
8. To determine skin gene expression changes that are associated with topical steroid response and non-response	13. Non-lesional and lesional skin tape transcriptome (non-AD and long-term dupilumab participants excluded)	8. Clinical response to topical steroids is associated with transcriptional profiles in the skin.
9. To determine skin gene expression changes that are associated with dupilumab response and non-response	14. Non-lesional and lesional skin tape transcriptome (dupilumab-naïve participants only) 15. Non-lesional and lesional skin biopsy transcriptome (adults only, dupilumab-naïve participants only)	9. Clinical response to dupilumab is associated with transcriptional profiles in the skin.
10. To determine the changes in cell type-specific gene and protein expression and cellular composition that are associated with dupilumab response and non-response	16. Single cell non-lesional and lesional skin biopsy transcriptome and proteome (dupilumab-naïve adults only)	10. Shifts in the cellular composition of skin and cell type-specific gene and protein expression changes underlie clinical response to dupilumab.
11. To determine whether AD skin endotypes are associated with topical steroid response	17. Non-lesional and lesional skin tape endotypes determined in exploratory objective 4	11. The clinical response to topical steroid treatment will be

Exploratory Objectives:	Related Endpoints:	Related Hypotheses:

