8.3 Baseline Assessment

The purpose of the Baseline Assessment is to confirm eligibility and conduct baseline clinical assessments, for study enrollment. Baseline Assessment will serve as Day 0 for scheduling the remaining trial activities. The following procedures and assessments will be conducted at the Baseline Assessment:

- Interim medical history
- Full physical examination
- Assessment of AD severity (EASI, IGA, SCORAD, NESS, PP-NRS, TAA, and targeted EASI), AD participants only
- Allergic disease questionnaires
- Confirm pregnancy status (if applicable), including performing a urine pregnancy test
- Assessment of concomitant medications
- Photographs will be taken of the selected and marked targeted skin areas (non-lesional and lesional, as applicable)
- Photographs will be taken of the measured lesional and non-lesional sites for collection of skin swabs and tape strips, as applicable
- Vital signs, including temperature, blood pressure, heart rate, and respiratory rate, and growth parameters (height and weight)
- Skin swab collection; up to 6 swabs

- STS collection; up to 40 STS
- Distribute Vanicream™ Moisturizing Cream
- Assessment of AEs

The Baseline Assessment can be completed on the same day as the Screening Visit; assessments that are completed at the Screening Visit will not be repeated.

Participants who do not meet inclusion and exclusion criteria due to assessment of their current medications/procedures will be asked whether they would be willing to come off their medications/procedures for a washout period. Participants who do not wish to washout of the prohibited medications/procedures will be identified as screen failures and will not continue in the study. Participants who are willing to washout of medications/procedures may repeat the Screening Visit once washout periods have been met.

At the conclusion of the Baseline Assessment, all eligible and enrolled participants will be instructed to apply Vanicream™ Moisturizing Cream twice daily to their target area to maintain adequate hydration of the epidermis and improve barrier function until their Day 7 Visit.

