Participants will be reminded to refrain from the use of prohibited medications/procedures as described in [Section 7.3](#). Participants will be given instructions regarding restrictions on bathing, showering, use of sunscreen, and use of moisturizers. For example, all participants will be instructed to avoid application of moisturizer (including Vanicream™ Moisturizing Cream) to their target area for 1 day prior to study visits; LTD participants will be further instructed to avoid application of moisturizer to any area on the upper/lower extremities or trunk for 1 day prior to study visits.

Use of chlorinated pools and hot tubs will also be prohibited 2 days prior to study visits. Individuals who can become pregnant, as defined in the study manual of procedures, will be instructed to use an acceptable method of contraception as described in [Section 4.2](#).

Participants will be provided with instructions on when to contact the research clinic should they experience any adverse events (AE). Contact information for the study physician and the 24-hour on-call physician will also be provided. The physician receiving the call will assess if the participant needs to be seen in clinic or if any further treatment is necessary.

Participant visit schedules after the Baseline Assessment will depend on the clinical group (e.g., steroid responders and non-responders) to which they are assigned.

8.4 1 Week Assessment (Steroid Initiation)

Participants of all clinical groups will have a visit at Day 7. For DNAD participants, the purpose of the 1 Week Assessment at Day 7 is to initiate treatment with topical steroids; this visit may be called the “Steroid Initiation.” Participants in other clinical groups have visits at this time so that Day 7 can serve as a standardized sampling point after consistent moisturization. The following procedures, assessments, and laboratory measures will be conducted at the visit:

- Interim medical history
- Physical examination (abbreviated at investigator discretion)
- Assessments of AD severity (EASI, IGA, SCORAD, PP-NRS, TAA, and targeted EASI), AD participants only
- Allergic disease questionnaires
- Confirm pregnancy status (if applicable), including performing a urine pregnancy test
- Assessment of concomitant medications

- Vital signs, including temperature, blood pressure, heart rate, and respiratory rate

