wide. Target area skin response will be measured by calculating the shift in two different AD severity scores between visits: the targeted area assessment (TAA) and targeted EASI. For body-wide assessment, we will both calculate the shift in EASI between visits as well as classify participants as either “responder” or “non-responder” if $EASI \leq 7$ or > 7 , respectively. We will then determine how topical moisturizer use is associated with skin expression changes and how these changes may differ based on clinical response to treatment by modeling gene expression both before and after treatment, using a linear mixed model based on normalized data that includes a participant-specific random intercept and fixed effects for visit, clinical response, disease group, and visit x clinical response interaction. Using this model, we will examine transcriptional responses to moisturizer by contrasting samples collected before and after treatment within AD disease groups. We will also examine differences in response to moisturizer based on clinical response by testing the interaction term. We will also construct models that predict different moisturizer clinical responses as a function of gene expression at Day 0. This will enable us to investigate any associations between clinical response to treatment and baseline expression. For each dataset, we will run different models using the four different clinical response measures (two continuous target lesional skin measures and both continuous and dichotomous body-wide measures). Note that clinical response measures from lesional skin will be used both in models with lesional skin gene expression and non-lesional skin gene expression.

Lesional and non-lesional skin, and children and adults will be modeled separately, after which expression changes in response to treatment with moisturizer will be compared between skin types and age cohorts.

Determining skin gene expression changes that are associated with topical steroid response and non-response [EO #8]

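### EO7 keeps non-AD participants, but its stated model needs a response score they never have and lacks the visit x disease group term its contrasts need

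*Protocol*

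**What the plan says.** Protocol Table 2.1.3 gives the EO7 endpoint as "12. Non-lesional and lesional skin tape transcriptome (long-term dupilumab participants excluded". The next endpoint, for EO8, reads "13. Non-lesional and lesional skin tape transcriptome (non-AD and long-term dupilumab participants excluded". Non-AD participants are thus removed by name from EO8 and left in EO7.

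Protocol 13.4.4, EO #7, describes one linear mixed model with a participant random intercept and "fixed effects for visit, clinical response, disease group, and visit x clinical response interaction". Response is measured in four ways: the shift in TAA, the shift in targeted EASI, the shift in body-wide EASI, and EASI at or below 7 versus above 7. For each dataset "we will run different models using the four different clinical response measures". The moisturizer effect is to be read by "contrasting samples collected before and after treatment within AD disease groups". Lesional and non-lesional skin, and children and adults, are modeled separately.

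The scores behind every response measure are limited to AD. Protocol 8.3 (Day 0) lists "Assessment of AD severity (EASI, IGA, SCORAD, NESS, PP-NRS, TAA, and targeted EASI), AD participants only", and 8.4 (Day 7) lists "Assessments of AD severity (EASI, IGA, SCORAD, PP-NRS, TAA, and targeted EASI), AD participants only". The non-AD schedule in Appendix A has no AD severity assessments. It does have the cream from Baseline to Day 7 and non-lesional tape transcriptomics at both visits.

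SAP 2.3 defers all exploratory objectives to a separate Exploratory SAP, which is not among the documents.

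**The concern.** The endpoint and the model describe different populations. A participant with no value for a fixed effect cannot contribute to a standard fit, so a group that the endpoint retains, and that was given cream and sampled at both visits, falls out of the analysis.

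The second gap is separate and would remain even if EO7 were meant for AD only. Before/after contrasts within disease groups require the visit effect to vary by disease group. In the stated model, disease group shifts only the level of expression. Secondary Objective 2, by contrast, includes visit x study outcome group for its within-group contrasts.

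At stake is whether EO7 can say how expression changes over the moisturizer period in mild AD, in moderate-to-severe AD and in skin without AD, and whether the change in AD differs from the change in non-AD skin.

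**Working it through.** **1. Enrollment targets (Protocol synopsis, Accrual Objective, and 13.7.1).**
- Non-AD: 100 adults + 50 children = 150.
- Dupilumab-naïve AD (DNAD): 160 + 80 moderate-to-severe, 100 + 50 mild = 390.
- Long-term dupilumab: 60.
- Check: 150 + 390 + 60 = 600, the plan's total.

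**2. Who is in EO7, and who can be fitted.** The endpoint population is 600 − 60 = 540. No EO7 sample size is stated, so this is a sum of approximate targets.

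| Non-lesional models | Endpoint population | With a response score | Lost |
|---|---|---|---|
| Adults | 100 + 260 = 360 | 260 | 100 (27.8%) |
| Children | 50 + 130 = 180 | 130 | 50 (27.8%) |
| Both | 540 | 390 | 150 (27.8%) |

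Fitting the stated terms to simulated data of these sizes, with rows lacking a response value removed, uses 260 of 360 adults and 130 of 180 children. The disease group factor keeps only its mild and moderate-to-severe levels, so no non-AD contrast can be estimated. The same holds for all four response measures. Non-AD participants give no lesional tape, so the lesional models lose nobody.

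**3. What the missing term does.** Write v for visit (0 before, 1 after), r for response and g for disease group. The stated model for mean expression is

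b0 + bV·v + bR·r + bG·g + bVR·v·r.

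The before/after change is bV + bVR·r, which does not contain g. At a given r, the difference in change between mild and moderate-to-severe AD is therefore zero by construction. Averaged over each group's own responses, the difference is bVR × (mean r in one group − mean r in the other). That need not be zero, but it can arise only through response.

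**4. The dichotomous measure.** Its cut, EASI at or below 7 versus above 7, is also the cut between mild and moderate-to-severe AD (Protocol 4.1; SAP 6.2, at the analysis timepoint). If both are taken at Day 7, response and disease group are the same variable in DNAD, and a visit x disease group term duplicates visit x response. If disease group is taken at Day 0, the two are separated only by participants who cross EASI 7 within about a week.

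**5. What exists elsewhere.** EO14 fits visit, outcome group and their interaction to all tape samples. It includes non-AD as a group and has no response term. Appendix A schedules Day 0 and Day 7 tape in both non-AD and DNAD participants. The Day 0 to Day 7 change in non-AD is therefore estimable in EO14, though the AD groups there are defined by later treatment outcome, not by severity.

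**The case against.** The strongest reply is that EO14 already supplies the non-AD comparison. This stands at study level. A reader might infer that the only AD-free comparison for the moisturizer week is lost, and the documents do not support that. They show only that EO7 does not deliver it by severity group.

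A reader might also infer that non-AD participants would separate the cream's effect from repeat tape stripping or batch. They would not, because they receive the cream and the stripping too. Subtracting their change isolates what is specific to AD, and a cream effect common to all skin is part of what EO7 asks about.

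A third tempting reading is that the model makes the change in the two severity groups identical outright. As shown above, equality is forced only at a fixed response value.

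It can also be said that the phrase about AD disease groups shows EO7 was meant for AD only, and that two of the four measures are target-area measures for lesional skin. If so, the endpoint's population still contradicts the model, and the missing interaction remains. Giving non-AD participants an EASI of 0 and a shift of 0 would keep them in, but no such rule is stated, and it would class every one of them as a moisturizer responder.

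Finally, the Exploratory SAP may settle this. That is a fair limit on what can be known. It does not cure the specific model in the protocol, which reserves only the analysis timepoints of exploratory objectives for the SAP.

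**Conclusion.** The point holds within these bounds. As written, EO7's non-lesional models cannot use the approximately 150 non-AD participants its endpoint retains (100 adults, 50 children; about 28% of roughly 540). Separately, its contrasts within AD disease groups are not properly group-specific, because the model has no visit x disease group term.

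This rests on approximate enrollment targets and on a standard fit that drops records with a missing covariate. The protocol states no rule for missing covariates in EO7 and assigns non-AD participants no response value. EO7 is exploratory and has no stated power, and the primary and secondary analyses are unaffected.

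**What to change.** In Protocol 13.4.4, EO #7, and consistently in the Exploratory SAP, specify two models, each fitted separately in adults and children:

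- **Model (a), change over the moisturizer period.** On non-lesional tape, include all participants outside the long-term dupilumab group. Use visit, disease group (non-AD, mild, moderate-to-severe, fixed at Day 0), visit x disease group and a participant random intercept, with no clinical response term. Use it for the change within each group and for AD change minus non-AD change. Fit the same model to lesional tape in DNAD only. Report the AD minus non-AD difference as AD-specific change, not as a cream effect freed of stripping or batch.
- **Model (b), clinical response.** Restrict the stated model to DNAD participants. Add visit x disease group (Day 0 severity) for the three continuous response measures only. Do not add it for the dichotomous EASI measure, where it is aliased with visit x response or nearly so.

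The cost is one extra model on samples already scheduled, plus one degree of freedom in the continuous-response models. No visit, sample or assay is added. If the sponsor intended EO7 for AD only, the endpoint in Table 2.1.3 should say so; model (a) would then run in DNAD alone, and the text should point to EO14 for the non-AD comparison.

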2.1 Study Objectives, Endpoints, and Hypotheses

Below are three tables (Tables 2.1.1 – 2.1.3) that include the 26 objectives and 35 related endpoints for the study, separated by priority and including the related hypotheses for each analysis. Endpoints will be collected based on enrollment group and treatment course as delineated in the schedules of events ([Appendix A](#)), and analysis timepoints for each exploratory objective will be noted in the statistical analysis plan (SAP).

Table 2.1.1. Primary Objective and Related Endpoint, Hypothesis

Primary Objective:	Related Endpoint:	Related Hypothesis:
1. To determine if the type 2-high non-lesional skin (skin tape) endotype is associated with current mild versus moderate-to-severe AD disease	1. Non-lesional skin tape transcriptome at Day 7 (long-term dupilumab participants excluded)	1. The type 2-high skin endotype in non-lesional skin is associated with severity of AD disease.

Table 2.1.2. Secondary Objectives and Related Endpoints, Hypotheses

Secondary Objectives:	Related Endpoints:	Related Hypotheses:
1. To determine how gene expression in the skin (skin tape) differs between non-AD participants and those with	1. Non-lesional and lesional skin tape transcriptome at Day 7 and Day 168-224 (long-term dupilumab participants excluded)	1. Distinct transcriptomic signatures detectable in tape collected skin underlie mild and moderate-to-severe AD.

Secondary Objectives:	Related Endpoints:	Related Hypotheses:
current mild or moderate-to-severe AD disease		
2. To determine how gene expression in the skin (skin tape) changes with standard-of-care treatment (two timepoints) among the study outcome groups: (1) topical steroid responders, (2) dupilumab responders, (3) dupilumab non-responders, (4) non-AD, and (5) long-term dupilumab participants	2. Non-lesional and lesional skin tape transcriptome at Day 7 and Day 168-224	2. The clinical response to protocol's standard-of-care treatment among different AD participants will be associated with distinct transcriptional shifts in tape collected skin over time.

Table 2.1.3. Exploratory Objectives and Related Endpoints, Hypotheses

Exploratory Objectives:	Related Endpoints:	Related Hypotheses:

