At the Baseline Assessment (Day 0), medical history, medication use, vital signs, and a pregnancy test (if applicable, as defined in the study manual of procedures) will be collected to confirm eligibility. Participants who meet eligibility after completing baseline study assessments will be considered enrolled. Several standard AD severity scoring measures will also be taken for participants who have AD (DNAD, LTD). Although the participant's AD will be monitored and treated body-wide over the course of the study, in consultation between the participant and investigator, a target skin region will be selected that will act as the controlled focal study area to be sampled, helping to facilitate compliance and consistency of topical treatment application which will be essential to the integrity of study outcomes. For this targeted region, an area will be selected to ensure availability of sufficient skin surface to sample as symptoms fluctuate over time and with treatment. In addition to body-wide measures of AD severity, targeted severity measures (targeted area assessment [TAA] and targeted EASI) will also be collected, enabling us to track clinical responses in AD severity to treatment within this more controlled target skin region.

Enrolled participants will be asked to begin applying Vanicream™ Moisturizing Cream (provided by the study) at least twice daily to the specified target area for approximately one week (until 1 day prior to their 1 Week Assessment/Steroid Initiation) and refrain from applying other moisturizers and topical steroids to the target skin area during this time. AD participants may apply topical steroids prescribed by their physician and moisturizer to non-target skin as needed during this time.

All enrolled participants will be permitted to apply Vanicream™ Moisturizing Cream to all other body sites as needed throughout the duration of the study.

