10. DNAD and LTD participants must have a history of chronic AD, (according to the Atopic Dermatitis Research Network [ADRN] Standard Diagnostic Criteria [[Appendix B](#)]), that has been present for at least 1 year before the Screening Visit.
11. DNAD and LTD participants must agree to refrain from applying topical steroid to a specified target area between the Baseline Assessment and Day 7 Visits.

DNAD Participants:

12. DNAD participants must have active lesions on the upper or lower extremities or trunk of sufficient size and in the required locations, as specified in the study manual of procedures (MOP), for specimen collection at the Baseline Assessment and Steroid Initiation (Day 7) Visits.

LTD Participants:

13. LTD participants must be currently receiving dupilumab and must have started dupilumab treatment ≥ 4 months prior to the Screening Visit.

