15. Individuals with asthma who have required use of a systemic corticosteroid within 3 months prior to the Screening Visit or who require a dose greater than 880 mcg/day of fluticasone propionate or equivalent inhaled corticosteroid to maintain asthma control
16. Treatment with biologics (other than dupilumab) as follows:
 - a. Any cell-depleting agents, including but not limited to rituximab, within 6 months before the Baseline Assessment, or until lymphocyte and CD19+ lymphocyte count returns to normal, whichever is longer
 - b. Omalizumab, infliximab, adalimumab, golimumab, certolizumab pegol, abatacept, etanercept, anakinra within 16 weeks before the Baseline Assessment for any indication
 - c. Other biologics within 5 half-lives (if known) or 16 weeks before the Baseline Assessment, whichever is longer

17. Ongoing participation in another research study involving any of the following:
 - a. Current or planned use of an investigational drug or device
 - b. Current or planned use of prohibited medications or procedures
 - c. Substantial time commitment and/or study requirements that, in the opinion of the investigator, may interfere with the participant's ability to comply with LEADS study requirements
18. Use of an investigational drug within 8 weeks or within 5 half-lives (if known), whichever is longer, before the Baseline Assessment
19. Use of topical calcineurin inhibitors (tacrolimus or pimecrolimus), topical phosphodiesterase inhibitors (crisaborole), topical JAK inhibitors (ruxolitinib), or topical Ahr agonists (tapinarof) within 1 week before the Baseline Assessment. Use of these medications is not exclusionary when only applied to the face, neck, palms, or soles.
20. Treatment with bleach bath within 1 week before the Baseline Assessment
21. Use of a chlorinated hot tub or pool within 1 week before the Baseline Assessment
22. Initiation of treatment with prescription moisturizers or moisturizers containing ceramide, hyaluronic acid, urea, or filaggrin (FLG) during the study.
 - a. Participants may continue using stable doses of such moisturizers on body areas other than the target area if initiated before the Baseline Assessment.
 - b. Initiation of prescription moisturizer is not exclusionary when only applied to the face, neck, palms, or soles.
23. Planned or anticipated use of any prohibited medications or procedures during study participation.

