2.3 Exploratory objectives

Not covered in this SAP, please refer to a separate Exploratory SAP.

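### EO7's before/after contrast in AD target skin combines the moisturizer effect with topical-steroid withdrawal, because steroid on that skin stops when moisturizer starts and no prior washout is stated

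*Protocol*

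**What the plan says.** For EO #7, Protocol Section 13.4.4 states that "we will examine transcriptional responses to moisturizer by contrasting samples collected before and after treatment within AD disease groups". The model is a linear mixed model with a participant random intercept and fixed effects for visit, clinical response, disease group and visit x clinical response. Clinical response is the shift in targeted EASI or in TAA on lesional target skin, or a body-wide EASI measure. The section also plans models predicting "moisturizer clinical responses as a function of gene expression at Day 0". LTD participants are excluded; NAD and DNAD participants remain.

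Day 0 is thus the pre-treatment sample. The post-treatment visit is not named. Section 8.4 says that groups other than DNAD also attend then so that "Day 7 can serve as a standardized sampling point after consistent moisturization". Section 2.1 leaves exploratory timepoints to the SAP, and SAP Section 2.3 says of exploratory objectives: "Not covered in this SAP, please refer to a separate Exploratory SAP".

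On target skin, Section 3.1 has participants start the study moisturizer at Baseline and "refrain from applying other moisturizers and topical steroids to the target skin area during this time". Under inclusion criterion 11 (Section 4.2), AD participants "must agree to refrain from applying topical steroid to a specified target area between the Baseline Assessment and Day 7 Visits". Exclusion criterion 19 (Section 4.3; number 25 in the synopsis) sets one week before Baseline for topical calcineurin, phosphodiesterase and JAK inhibitors and AhR agonists. Topical corticosteroids are not on that list, and the other steroid exclusions concern systemic or inhaled use.

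**The concern.** Two or three things change on AD target skin at the same visit. Study moisturizer starts, any topical steroid stops, and any other moisturizer stops. EO7 attributes the resulting change to the first. A DNAD participant who had been treating that skin would give the Day 0 tape under steroid and the Day 7 tape after a week without it.

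The same mixture enters the targeted EASI and TAA shifts that serve as clinical response, so the visit x clinical response term is also hard to read as response to moisturizer. If withdrawal lets steroid-suppressed genes rise again, it could hide a moisturizer benefit or look like a moisturizer effect. The documents do not establish the direction for any gene.

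The protocol recognizes this kind of problem: Section 7.3.1 warns that samples taken during use or washout of a prohibited medication often lose much of their value.

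**Working it through.** **1. No figure to reproduce.** The documents give no sample size, power or effect size for EO7. The check is of design logic, followed by an illustration of size.

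**2. The timeline.**
- The target area is chosen at Baseline, and Screening may fall on the same day (Section 3.1). A rule tied to that area cannot begin before Day 0.
- The required steroid-free period on the target area runs from Baseline to Day 7 only.
- From Day 0 to Day 7, AD participants may still use prescribed topical steroid on non-target skin (Section 3.1). A body-wide medication record therefore does not show whether the sampled area had been treated.
- Moving the contrast to Day 140 to 168 would not help topical steroid responders. They stop steroid on active lesions in the target area at Day 140, when moisturizer restarts (Section 3.1.1).

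**3. What the visit contrast estimates.** Let U = 1 if a participant recently used topical steroid on the target area, and 0 otherwise. Let m be the moisturizer effect and w the withdrawal effect on a gene, both in log2 units. Then

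change from before to after = m + w x U,

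and the mean over participants is m + s x w, where s is the share of users. The bias is s x w.

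A main effect g x U adds the same amount at both visits and cancels in the difference. So does the random intercept. With a visit x U term, the visit contrast at U = 0 is m, apart from any change of moisturizer.

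**4. Size under assumptions.** Neither s nor w is in the documents. With w = 0.5:
- s = 0.2: 0.2 x 0.5 = 0.10 log2, and 2^0.10 = 1.07.
- s = 0.6: 0.6 x 0.5 = 0.30 log2, and 2^0.30 = 1.23.

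The bias is linear in w, so the table varies both. With W = 2^w the withdrawal fold change and no moisturizer effect at all, the apparent moisturizer fold change is W^s:

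| W | s = 25% | s = 50% | s = 75% |
|---|---|---|---|
| 1.25 | 1.06 | 1.12 | 1.18 |
| 1.5 | 1.11 | 1.22 | 1.36 |
| 2.0 | 1.19 | 1.41 | 1.68 |

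The share s probably differs between lesional and non-lesional skin, which EO7 models separately. One value should not be applied to both.

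**5. Could a bias of this size be declared significant?** The formula behind Table 13.7.1.3 is

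FC = exp( sqrt( (z for alpha/2 + z for 80% power)^2 x (1/depth + CV^2) x (1/n1 + 1/n2) ) ),

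with alpha = 0.05/10,000, depth 10 and CV 0.4. The squared sum of z values is about 29.2, and 1/10 + 0.4^2 = 0.26, so their product is about 7.60. For n = 175 this gives exp(sqrt(7.60 x 2/175)) = 1.34, the protocol's own figure; n = 34 gives 1.95, also as printed.

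Applied to a two-visit contrast at target enrollment, the minimum detectable fold changes are:
- 260 AD adults: exp(sqrt(7.60 x 2/260)) = 1.27
- 160 moderate-to-severe adults: 1.36
- 100 mild adults: 1.48
- 130 AD children: 1.41

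The formula ignores pairing, so these are indicative only. On these figures, withdrawal alone could produce significant genes in the upper part of the assumed range (for example 1.41 or 1.68 against 1.27), but not in the lower part.

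**The case against.** The strongest reply has four parts.

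- **Missing documents.** The timepoints belong to the Exploratory SAP, and Section 7.3.1 places washout periods for prohibited medications in the MOP. Section 7.3 lists non-study topical steroid on arms, legs and trunk as prohibited for DNAD participants. Either document could already deal with this. That stands: Day 0 to Day 7 is an inference, and steroid use up to Baseline is inferred from silence in the eligibility lists, not from a stated permission.
- **Existing mitigation.** Section 13.1 allows concomitant therapies as covariates and, where these are significant, promises sensitivity analyses on stratified data. Concomitant medications are already collected at Screening and Baseline. Stratifying by user status would separate the two changes. This stands in part. The provision is conditional on significance and not specific to the target area, and an optional main effect does not touch the visit contrast.
- **Non-AD participants.** They stay in EO7 and show change under moisturizer without steroid withdrawal. But theirs is non-AD skin, and the stated contrast is within AD groups, so they do not isolate the effect.
- **Weight.** EO7 is one of 23 exploratory objectives, is worded as association, and the size above rests wholly on assumed inputs. All of that stands, and it limits the importance of the point.

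A reader might also infer a spurious difference in moisturizer response between mild and moderate-to-severe AD, on the view that sicker participants use more steroid. The documents do not support this: EO7 has no visit x disease-group term and states no such comparison of change, and use by severity is not documented. Nor does the argument carry over to the models predicting response from Day 0 expression. They contain no before/after expression contrast, so s x w does not apply, and any confounding there would need its own argument.

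**Conclusion.** The point holds as a limit on interpretation. Following the protocol text, EO7 cannot attribute the change in DNAD target-skin expression, or the targeted EASI and TAA shifts, to moisturizer alone in participants who recently used topical steroid there. Participants without such use are not affected by withdrawal.

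The size is unknown. It equals s x w, with both quantities assumed, and runs from negligible to large enough to reach significance. The conclusion assumes that the post-treatment sample is Day 7, that some DNAD participants treat the chosen area shortly before Baseline, and that the MOP imposes no steroid washout.

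A reader might extend the point to the main results. That does not follow: the primary objective uses Day 7 samples only, and neither secondary objective uses the Day 0 to Day 7 change.

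**What to change.** - **Baseline eCRF:** record the date of last topical steroid use, and of last use of any other moisturizer, on the chosen target area.
- **EO7 model:** add recent target-area steroid use and its interaction with visit.
- **EO7 reporting:** give the moisturizer contrast for participants with no steroid on that area in the 7 days before Baseline, alongside the full set and separately for lesional and non-lesional skin. The 7 days mirror the interval already applied to the other topical classes and serve here only to define an analysis subset. Attribute the change to moisturizer only where the non-user estimate supports it.
- **Exploratory SAP:** name the two visits. If the MOP already requires a topical-steroid washout, a sentence in EO7 saying so is enough.

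The cost is one eCRF item, some EO7 wording and a less precise estimate in non-users. Keeping the full set in view avoids resting the objective on a smaller, selected subset. Restricting to steroid non-users does not remove a switch from another moisturizer, which is why that date is worth recording too. Eligibility, treatment and visits do not change.
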